3.4.2 Secondary Efficacy Endpoints

Similar ANCOVA models as described for the primary analyses will be used to analyze the secondary efficacy endpoints and will be tested sequentially at the 0.05 significant level according to the order specified below:

- Percentage change from Baseline to Days 180 and 365 in LDL-C in the obicetrapib group compared to the placebo group;
- Percentage change from Baseline to Days 84, 180, and 365 in ApoB in the obicetrapib group compared to placebo group;
- Percentage change from Baseline to Days 84, 180, and 365 in non-HDL-C in the obicetrapib group compared to placebo group;
- Percentage change from Baseline to Days 84, 180, and 365 in HDL-C in the obicetrapib group compared to placebo group;
- Percentage change from Baseline to Days 84 and 365 in Lp(a) in the obicetrapib group compared to placebo group;
- Percentage change from Baseline to Days 84, 180, and 365 in TC in the obicetrapib group compared to placebo group;
- Percentage change from Baseline to Days 84, 180, and 365 in TG in the obicetrapib group compared to placebo group.

For the percentage change from Baseline to Day 180 in LDL-C, the LDL-C will be calculated using the Friedewald equation unless the Triglyceride value is ≥ 400 mg/dL or the LDL-C value is ≤ 50 mg/dL; in which case, the LDL-C level measured directly by PUC will be used in the analysis. The latter approach will be used because PUC assessments are not performed at Day 180 as per the protocol, unless the conditions for Triglycerides or LDL-C described above are met at the Day 180 assessment. The analysis will be repeated using the Martin-Hopkins equation as described in the [Section 3.4.1](#) above.

3.4.3 Exploratory Efficacy Endpoints

Similar ANCOVA models as described for the primary analyses will be used to assess the percentage change from Baseline to Day 84 and 365 in fasting ApoA1 in the obicetrapib group compared to the placebo group.

The proportion of participants at Days 84 and 365 who achieved

- LDL-C levels of <40 mg/dL (<1.04 mmol/L), <55 mg/dL (<1.42 mmol/L), <70 mg/dL (1.81 mmol/L), and <100 mg/dL (<2.59 mmol/L) at Days 84 and 365;
- non-HDL-C levels of <85 mg/dL (<2.20 mmol/L), <100 mg/dL (<2.59 mmol/L), and <130 mg/dL (<3.37 mmol/L) at Days 84 and 365;
- ApoB levels of <65 mg/dL (<0.65 mmol/L), <80 mg/dL (<0.80 mmol/L), and <130 mg/dL (<1.30 mmol/L) at Days 84 and 365

in the obicetrapib group compared to the placebo group, will be examined using logistic regression models with covariates of treatment group and respective Baseline values as covariates. Odds ratio with 95% confidence intervals will be estimated.

The logistic regression model will be implemented using SAS® Proc LOGISTIC. The sample SAS code can be found below:

```
*****
```

Note:

TREATMENT = 0 (Placebo), 1 (Obicetrapib)
BASE = Baseline LDL_C value
LDLC40 = LDL_C value less than 40mg/dL at DAY84 (YES/NO) for example

```
*****
```

```
proc logistic data= LDL_C;  
  Class TREATMENT(ref=0) / Param= Ref;  
  Model LDLC70= TREATMENT BASE / alpha=0.05 expb plcl plrl orpvalue lackfit;  
  Ods output  
    ParameterEstimates= Log_LDLC40_ParameterEstimates  
    CLoddsPL= Log_LDLC40_OddsRatios  
    ;
```

Run;

```
*****
```

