2.2 Study Design

2.2.1 *Overview*

This study is a multisite, placebo-controlled, double-blind, randomized Phase 3 study in approximately 300 participants with a history of HeFH who are not adequately controlled by their lipid-modifying therapy to evaluate the efficacy, safety, and tolerability of obicetrapib.

Approximately 300 eligible participants will be randomized in a 2:1 ratio, respectively, to the

following treatment groups:

- Obicetrapib group: one 10 mg obicetrapib tablet once daily; or
- Placebo group: 1 placebo tablet once daily.

At least 70% of the participants enrolled into this study must be taking high intensity statins (HISs). HeFH diagnosis is defined by existing confirmation via genetic testing, WHO Criteria/Dutch Lipid Clinical Network (DLCN) Criteria with a score of >8 points, and/or Simon Broome Register Diagnostic Criteria [1,2].

Starting on Day 1, each participant will self-administer their assigned study drug once daily until Day 365. During the Treatment Period, participants will return to the study site for efficacy and safety assessments. Blood samples for pharmacokinetic (PK) assessment will be collected at specified visits throughout the study. The End Of Study (EOS) Visit will be conducted approximately 35 days after the participant's last dose of study drug, during which vital signs; limited serum chemistry, hematology, and coagulation parameters; pharmacokinetics; concomitant medications; and AEs will be assessed.

The study drug blind will be maintained through the EOS Visit (Visit 8). Participants, the Sponsor, Investigators, and all study site personnel involved in the study, including personnel carrying out study procedures, evaluating participants, entering study data, and/or evaluating study data, will remain blinded to treatment allocations until all participants have completed the EOS Visit assessments and the database has been locked for analysis.

Active and placebo products will be identical. Medication bottles with a unique code will be assigned to participants at various points in the study by the Medpace Interactive Response Technology system.

Refer to [Table 1 Schedule of Procedures](#) for a complete list of procedures to be completed at each study visit.

Table 1 Schedule of Procedures

Visit	Screening		Treatment Period					EOS
	V1	V2	V3	V4	V5	V6	V7/EOT/ET ¹	
Study Day	-14 to -1	1	30	84	180	270	365	35 days after last dose
Window (±days)	±3		±3	±7	±7	±7	±7	±7
Informed consent	X							

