7. A single 12-lead ECG will be performed in the supine position after 10 minutes of rest.
8. Participants must fast for a minimum of 8 hours prior to samples being collected.
9. Samples should be collected prior to study drug administration.
10. Urinalysis will be performed locally by dipstick analyses from a sample of mid-stream urine. In case of abnormal results, microscopy and other assessments will be performed at the local laboratory and the abnormality recorded as an AE.
11. A PK sample will be collected prior to study drug administration for trough measurement of obicetrapib in plasma. At Visits 2, 5, and 7, participants should take study drug after a trough PK sample has been drawn.
12. The PK sample at Visit 4 is not designated in the protocol, however the PK will be assessed using residual serum from the Day 84 limited chemistry panel to confirm patients are taking IP.

AE = adverse event; ApoA1 = apolipoprotein A1; BMI = body mass index; CV = cardiovascular; ECG = electrocardiogram; EOS = End of Study; EOT = End of Treatment; ET = Early Termination; FSH = follicle-stimulating hormone; hsCRP = high sensitivity C-reactive protein; Lp(a) = lipoprotein (a); PK = pharmacokinetic(s); TSH = thyroid-stimulating hormone; UACR = urine albumin-creatinine ratio; UPCR = urine protein-creatinine ratio; V = Visit.

2.2.2 *Sample Size Determination*

Enrollment of approximately 300 participants globally is planned for this study.

Assuming an approximate 5% drop out rate, approximately 285 participants will be evaluable for efficacy. This sample size of at least 285 evaluable participants will provide more than 90% power to detect a 30% reduction of LDL-C (standard deviation 15%) levels in the obicetrapib group compared to the placebo group at a 1-sided significance level of 0.025. This sample size will also contribute to sufficient participant exposure and safety data.

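### At LDL-C below 40 mg/dL on Day 84 the planned odds ratio will probably not be finite, and the sample SAS code models the wrong response level and mismatches its threshold names

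*SAP*

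**What the plan says.** SAP 3.4.3 compares goal attainment at Days 84 and 365 for four LDL-C, three non-HDL-C and three ApoB thresholds. That is (4 + 3 + 3) × 2 = 20 models. Each "will be examined using logistic regression models with covariates of treatment group and respective Baseline values as covariates", and each is to yield an odds ratio with a 95% confidence interval. The section gives no rule for empty or sparse cells.

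The section's sample PROC LOGISTIC code defines its response as "LDLC40 = LDL_C value less than 40mg/dL at DAY84 (YES/NO) for example". The fitted statement begins "Model LDLC70= TREATMENT BASE", and both output datasets carry LDLC40 in their names. The code requests profile-likelihood limits. It contains no event= or DESCENDING option and no FIRTH option.

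**The concern.** Entry requires LDL-C of at least 70 mg/dL at Screening (Protocol 4.1, criterion 5). A placebo participant starting at that floor must fall by 30/70 = 42.9% to get below 40 mg/dL. If nobody on placebo does so and somebody on obicetrapib does, the data show quasi-complete separation: the likelihood keeps rising as the treatment coefficient grows, so there is no finite odds ratio. A profile-likelihood interval then has at most one finite limit. With no rule in the SAP, the choice between a penalised fit, an exact method and omission would be made after unblinding.

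The coding matters separately. PROC LOGISTIC by default models the first response level in sort order, and NO sorts before YES. If the template is reused, every odds ratio describes the odds of missing the goal. Run as written, results for below 70 mg/dL would also be filed under a below-40 name.

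**Working it through.** **Inputs from the documents.** SAP 2.2: "Approximately 300 eligible participants will be randomized in a 2:1 ratio"; "Assuming an approximate 5% drop out rate, approximately 285 participants will be evaluable for efficacy"; the sample size "will provide more than 90% power" for a 30% reduction with SD 15%, "at a 1-sided significance level of 0.025".

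**The plan's own figure.** 300 × 0.95 = 285, which splits 2:1 into 190 and 95. The standard error is 15 × √(1/190 + 1/95) = 1.885, and 30/1.885 = 15.9. Power is Φ(15.9 − 1.96) ≈ 1.00, so the stated figure is reproduced. The documents give no expected responder counts.

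**Chance of no placebo responder below 40 mg/dL.** Assume a normal percent change with mean 0. For Baseline B, p = Φ((40/B − 1)/SD) and P(zero of 95) = (1 − p)^95.

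| Every Baseline at (mg/dL) | SD 15%: p | SD 15%: P(zero) | SD 20%: p | SD 20%: P(zero) |
|---|---|---|---|---|
| 70 | 0.0021 | 0.82 | 0.0161 | 0.21 |
| 80 | 0.0004 | 0.96 | 0.0062 | 0.55 |
| 90 | 0.0001 | 0.99 | 0.0027 | 0.77 |
| 100 | 0.00003 | 0.997 | 0.0013 | 0.88 |

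For example, at 70 mg/dL and SD 15%, Φ(−0.4286/0.15) = Φ(−2.857) = 0.0021, so 95 × 0.0021 = 0.20 responders are expected.

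**Spread of Baselines (assumed).** I took lognormal values with mean 100 to 130 and SD 30 to 50 mg/dL, dropped those below 70, and ran this with and without 10% variation between Screening and Day 1:

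- SD 15%: P(zero) about 0.96 to 0.997
- SD 20%: about 0.70 to 0.93
- SD 25%: roughly 0.3 to 0.6
- SD 30%: below about 0.3

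A mean placebo change of −5% with everyone at the floor and SD 15% gives p = Φ((−0.4286 + 0.05)/0.15) = Φ(−2.524) = 0.0058 and P(zero) = 0.58.

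**Obicetrapib arm.** With a mean change of −30% and SD 15%, the same Baselines give about 2 to 9 expected responders of 190. Separation is therefore the normal outcome. At the low end (2.4 expected), both arms are empty with probability about exp(−2.4) = 0.09, and then nothing can be fitted.

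**What the fit returns.** In a simulated trial with 0/95 against 4/190 responders, the maximum-likelihood odds ratio ran above 10^11 modelling YES and below 10^−11 modelling NO. Firth's method gave 4.0 (Wald 95% interval 0.24 to 68). With 0/95 against 5/190 it gave 8.1 (0.41 to 157).

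**Other thresholds.** For LDL-C below 55 mg/dL over the same Baselines, P(zero) is about 0.04 to 0.88 across SD 15% to 20%. Below 70 mg/dL it does not exceed about 0.2 at SD 15%. I made no calculation for non-HDL-C or ApoB. No SD is stated for Day 365.

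**Event level.** In simulated data for below 70 mg/dL (8/95 against 91/190), the odds ratio was 24.1 modelling YES and 0.041 modelling NO, and 1/24.1 = 0.041.

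**The case against.** - **Scope.** A reader might infer that goal-attainment models in general will break down. The documents do not support that. The argument holds for LDL-C below 40 mg/dL, which is 2 of the 20 models, and only the Day 84 one can be assessed. Below 55 mg/dL it may apply.
- **Assumptions.** The documents state no Baseline distribution and no placebo mean change. The 70 mg/dL rule applies at Screening, by the Friedewald equation. Baseline is the last pre-dose value, measured by ultracentrifugation at Visit 2 (Protocol 7.1), and SAP 3.3.4 itself lists a Baseline category below 70. The floor is therefore not a strict bound. At SD 20% the floor alone would not carry the point (0.21); Baselines well above it are needed. Protocol 8.7.4 also allows lipid therapy to be intensified after confirmed high values, which could widen the placebo tail by Day 365. All of this stands, and limits the claim to Day 84 with an SD near 15% to 20%.
- **Partial delivery.** One profile-likelihood limit may be finite, and Protocol 9.2.1.2 promises descriptive summaries by group, so a count of 0 of 95 should still appear. That is correct, but it does not supply the promised odds ratio and two-sided interval.
- **The code is a sample.** SAP 7 leaves detailed programming to a separate document, and the prose of 3.4.3 makes the event attainment of the goal. A reader might infer that reversed results will be reported; the documents do not show that. A reversed odds ratio is also an exact reciprocal, so no information is lost. The SAP text is still wrong as printed.

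**Conclusion.** The point holds in limited form. Under the planning SD of 15%, approximate normality and a mean placebo change of 0, zero placebo responders below 40 mg/dL at Day 84 is likely: 0.82 at the floor and about 0.96 to 0.997 for the assumed Baseline spread. It remains likely at SD 20% over that spread, and is no longer usual at SD 25% or more. The treatment odds ratio then tends to 0 if NO is modelled and to infinity if YES is modelled, so correcting the event level alone does not cure it. Below 55 mg/dL may be affected, Day 365 cannot be judged, and no other threshold has been shown to be affected.

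The coding faults are independent of these assumptions: an unnamed event level that defaults to NO, and LDLC70 results filed as LDLC40. A reader might infer a threat to the trial's main findings. There is none, because these endpoints are exploratory and outside the testing sequence (SAP 3.1.6). This is a minor correction.

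**What to change.** In the SAP 3.4.3 sample code, specify event='YES' and make the response variable match the output dataset names.

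In the text, prespecify that any threshold with a zero or sparse cell in either group, with sparse defined by a stated count, is fitted by Firth-penalised likelihood with penalised profile-likelihood limits. Report the responder counts alongside. A difference in proportions with a score interval is a useful optional addition. Also say what will be reported if neither group has a responder.

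The cost is one sentence of text, one model option and corrected sample code; no new data are needed. The downside is a small shrinkage of the odds ratio, confined to the sparse models. Applying Firth's method to all 20 models would go further than the problem requires.

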3.4.4 Subgroup Analysis

The primary efficacy endpoint also will be analyzed by the following subgroups:

- Age categories (<65 years, 65 to 74 years, and 75+ years)
- Sex (male, female)
- Race (white, Asian, Black or African American, Other)
- Ethnicity (Hispanic/Latino, Not Hispanic/Latino)
- BMI (<25 kg/m², 25 -30 kg/m², ≥30 kg/m²)
- Region (North America and EMEA (Europe, Middle East, and Africa))
- Diabetes (yes, no)
- HDL-C (<40mg/dL, 40 - <60 mg/dL, ≥60mg/dL)
- ApoB (<60mg/dL, 60 - <90 mg/dL, ≥90mg/dL)
- ApoA1 (<110 mg/dL, ≥110 and <125 mg/dL, ≥125mg/dL)
- Lipoprotein(a) (<75nmol/L, ≥75 and <125 nmol/L, ≥125nmol/L)
- Non-HDL-C (<100 mg/dL, ≥100 and <130 mg/dL, ≥130mg/dL)
- LDL-C (<70mg/dL, ≥70 and <100 mg/dL, ≥100mg/dL)
- TG (<150 mg/dL, ≥150mg/dL)
- HbA1c (<5.7%, ≥5.75 to ≤6.4%, >6.4%)
- Urinary albumin:creatinine ratio (normal, micro-albuminuria, macro-albuminuria)
- eGFR (<60ml/min/1.73 m², ≥60 to <90ml/min/1.73 m², ≥90ml/min/1.73 m²)
- Statin treatment (high dose, low or moderate dose, none)
- Ezetimibe use (yes, no)
- Hs-CRP (<2mg/dL, ≥2mg/dL)
- HeFH (Genotyping confirmed or DLCN>8 points of Simon Broome definite; Simon Broome possible FH diagnosis)

The ANCOVA model with fixed effects for the treatment group, subgroup variable, treatment-by-subgroup variable and covariates of Baseline LDL-C will be used. The least squares (LS) mean, standard errors, and 2-sided 95% confidence intervals for each treatment group and for the mean difference compared to placebo, within each level of the subgroup, will be estimated. No imputation of missing data will be performed; therefore, the subgroup analysis will be performed

using only observed data. For the primary efficacy endpoint, the LDL-C values measured by PUC will be used. However, if the analysis for the primary efficacy endpoint specified above will show a difference between the 3 LDL-C approaches, then Friedewald and Martin-Hopkins equations may be considered for subgroup analysis.

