3.3.4 Demographic and Baseline Characteristics

The following demographic and Baseline characteristics will be summarized with descriptive statistics or counts and percentages of participants as appropriate by treatment group and overall, for the ITT Population:

- Age and age categories (<65 years, 65 to 74 years, and 75+ years)
- Sex
- Race
- Ethnicity
- Height
- Weight
- Body Mass Index (BMI)
- Region (North America and EMEA (Europe, Middle East, and Africa))
- Diabetes (yes, no)
- HDL-C (<40mg/dL, 40 - <60 mg/dL, ≥60mg/dL)
- ApoB (<60mg/dL, 60 - <90 mg/dL, ≥90mg/dL)
- ApoA1 (<110 mg/dL, ≥110 and <125 mg/dL, ≥125mg/dL)
- Lipoprotein(a) (<75nmol/L, ≥75 and <125 nmol/L, ≥125nmol/L)
- Non-HDL-C (<100 mg/dL, ≥100 and <130 mg/dL, ≥130mg/dL)
- LDL-C (<70mg/dL, ≥70 and <100 mg/dL, ≥100mg/dL)
- TG (<150 mg/dL, ≥150mg/dL)
- HbA1c (<5.7%, ≥5.75 to ≤6.4%, >6.4%)
- Urinary albumin:creatinine ratio (normal, micro-albuminuria, macro-albuminuria)
- eGFR (<60ml/min/1.73 m², ≥60 to <90ml/min/1.73 m², ≥90ml/min/1.73 m²)
- Statin treatment (high dose (HIS), low or moderate dose (non-HIS), none (SI)). High dose statin includes atorvastatin 40 or 80 mg, rosuvastatin 20 or 40 mg. Participants will be defined as having high dose statin treatment based on the data collected in the eCRF and if any following were used at Baseline: average daily dose of atorvastatin ≥40 mg or average daily dose of rosuvastatin of ≥20 mg. Additionally, these medications can be a part of combination medications (e.g. Rosuzet 10/20mg; combination of ezetimibe 10mg and Rosuvastatin 20mg). Participants having other doses of statin or other statin treatment will be defined as low or moderate (non-HIS). Participants that are not taking statin are defined as statin intolerant (SI).
- Ezetimibe use (yes, no)
- A high-sensitivity C-reactive protein [hs-CRP] (<2mg/dL, ≥2mg/dL)
- HeFH (Genotyping confirmed or DLCN>8 points of Simon Broome definite; Simon Broome possible Familial Hypercholesterolemia (FH) diagnosis)

If they differ from the ITT Population, summaries will also be provided for the FAS, the mITT Population, the mITT On-Treatment, the PP Population, and the Safety Population. Demographic characteristics data will be provided in participant listings.

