Vital signs (heart rate and blood pressure) measured in triplicate prior to study administration at applicable visits as indicated in Table 1. Values will be summarized with descriptive statistics, including the change from Baseline at each visit by treatment group and overall.

Additional summaries of blood pressure measurements will be performed, within treatment group and time point, using counts of triplicate means that meet the following criteria:

- Systolic blood pressure:
 - ≥ 160 mmHg
 - ≥ 180 mmHg
 - change from Baseline by ≥ 20 mmHg
- Diastolic blood pressure:
 - ≥ 100 mmHg
 - ≥ 110 mmHg
 - change from Baseline by ≥ 15 mmHg.

As described above, the number and percentage of participants receiving antihypertensive medications at Baseline with changes to antihypertensive medications due to change in blood pressure will be summarized by treatment group. The number of participants who were not hypertensive or on any antihypertensive medications at Baseline, but started one or more antihypertensive drugs during the treatment period, will be summarized by treatment group.

Vital signs will be listed.

3.5.5 *Electrocardiograms*

A single 12-lead ECG will be performed at Visit 2 and Visit 7/EOT/ET and will be read locally.

ECG parameters will be recorded as normal, abnormal or not done. Abnormal values will be assessed as clinically significant or not clinically significant. Counts and percentages for ECG parameters will be summarized by treatment group and in total.

3.5.6 *Physical Examinations*

Physical examinations (with focused examination on general, respiratory, CV, abdominal, and extremities evaluations) and recording of weight and height will be performed at Screening Visit and Visit 7/EOT/ET. Height will be measured at Screening Visit only and used to calculate body mass index. BMI will be calculated as weight/(height/100)² (kg/m²); rounded and displayed to 1 decimal place.

Physical examination, parameters, will be recorded as normal, abnormal or not done. Abnormal values will be assessed as clinically significant or not clinically significant. Count and percentages for physical parameters will be summarized by treatment group and in total.

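### HbA1c values from 5.70% to below 5.75% fall in no category in SAP 3.3.4 and 3.4.4

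*SAP*

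**What the plan says.** SAP 3.4.4 lists the subgroups for the primary endpoint. HbA1c appears there as "HbA1c (<5.7%, ≥5.75 to ≤6.4%, >6.4" (the quote stops just before the closing percent sign). The same three groups stand in the baseline characteristics list in SAP 3.3.4.

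The model in 3.4.4 uses each grouping as one factor: "The ANCOVA model with fixed effects for the treatment group, subgroup variable, treatment-by-subgroup variable and covariates of Baseline LDL-C will be used". Every participant therefore needs exactly one level of each factor.

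Two other entries in 3.4.4 bear on the same edit:

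- BMI is given as "BMI (<25 kg/m², 25 -30 kg/m², ≥30 kg/m²". SAP 3.5.6 says BMI is "rounded and displayed to 1 decimal place". BMI is not categorised in 3.3.4.
- hs-CRP is given as "Hs-CRP (<2mg/dL, ≥2mg/dL", and in 3.3.4 as "A high-sensitivity C-reactive protein [hs-CRP] (<2mg/dL, ≥2mg/dL".

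For comparison, HDL-C in the same list is written "HDL-C (<40mg/dL, 40 - <60 mg/dL, ≥60mg/dL", with the middle group closed below and open above.

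**The concern.** A set of categories should place every possible value in exactly one group. The HbA1c set does not. The lower bound of its middle group reads 5.75 with no percent sign, while the other HbA1c bounds carry one. It looks like 5.7% with the percent sign mistyped as a 5.

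A participant with no level of the factor is left out of a model that contains it. The losses would all sit next to one boundary, and nothing in the output would flag them except a baseline column that fails to add up. A programmer who notices the gap must choose a side outside the prespecified plan. The protocol offers no fallback, because SAP Section 6 records that subgroup analysis was added by the SAP.

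**Working it through.** The plan states no figure on this point, so there is none to reproduce. The check is whether each set of groups is exhaustive and non-overlapping, followed by a rough size.

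**1. HbA1c, logic.** Testing every value from 4.00 to 10.00 against the three conditions:

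- In steps of 0.01: 5.70, 5.71, 5.72, 5.73 and 5.74 meet no condition, and no value meets two.
- In steps of 0.1: only 5.7 meets no condition.
- With the middle group rewritten as ≥5.7 to ≤6.4: every value meets exactly one condition.

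**2. HbA1c, size.** The planned number is about 300 (SAP 2.2.1: "Approximately 300 eligible participants will be randomized in a 2:1 ratio"). The distribution is my assumption: normal, mean 5.5, 5.7 or 5.9, SD 0.4, 0.6 or 0.8.

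- One-decimal reporting: a value is reported as 5.7 if it lies between 5.65 and 5.75, so expected n = 300 × [Φ((5.75 − mean)/SD) − Φ((5.65 − mean)/SD)].
- Two-decimal reporting: 5.70 to 5.74 corresponds to 5.695 to 5.745, with the same formula.

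Largest case, one decimal (mean 5.7, SD 0.4): Φ(0.125) − Φ(−0.125) = 0.5497 − 0.4503 = 0.0995 before rounding the terms, and 300 × 0.0995 = 29.8.

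Smallest case, one decimal (mean 5.5, SD 0.8): Φ(0.3125) − Φ(0.1875) = 0.6227 − 0.5744 = 0.0483, and 300 × 0.0483 = 14.5.

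| Mean | SD | n of 300, one decimal | n of 300, two decimals |
|---|---|---|---|
| 5.5 | 0.4 | 26.4 | 12.9 |
| 5.5 | 0.6 | 18.8 | 9.3 |
| 5.5 | 0.8 | 14.5 | 7.2 |
| 5.7 | 0.4 | 29.8 | 14.9 |
| 5.7 | 0.6 | 19.9 | 10.0 |
| 5.7 | 0.8 | 15.0 | 7.5 |
| 5.9 | 0.4 | 26.4 | 13.5 |
| 5.9 | 0.6 | 18.8 | 9.5 |
| 5.9 | 0.8 | 14.5 | 7.3 |

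With 2:1 allocation, about one third of these would be on placebo: roughly 5 to 10 participants with one decimal, or 2 to 5 with two.

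**3. BMI.** In steps of 0.1 from 15.0 to 60.0, the only problem value is 30.0. It meets two conditions if the dash is read as including 30. With 25 to <30 every value meets exactly one. Under assumed normal distributions (mean 27, SD 4.5; mean 29, SD 5; mean 30, SD 5.5), the expected number at 30.0 is 2.1, 2.3 and 2.2 of 300.

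**4. hs-CRP.** 2 mg/dL × 10 = 20 mg/L. The documents give no reporting unit, expected level or distribution. Under assumed lognormal values with median 1 to 3 mg/L and log-SD 1.0 to 1.2, the expected number at or above 20 mg/L runs from 0.4 to 17 of 300. With medians 1, 1.5, 2 and 3 mg/L and log-SD 0.9, 1.1 and 1.3, it runs from 0.1 to 22. In that wider grid, the chance that the upper group is completely empty exceeds one half in 2 of the 12 scenarios.

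**The case against.** The strongest reply is that little depends on this. Subgroup results lie outside the fixed testing sequence (SAP 3.1.6 and 3.4.2), and SAP Section 7 promises separate programming specifications, where an unassigned 5.7% would probably surface. The first part stands and sets the severity. The second does not cure the SAP, which is where the groups are prespecified. A slip in converting the PDF to text is unlikely, because the same string occurs in both sections and the other percent signs on the line are intact.

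Three stronger readings are tempting, and the documents do not support them:

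- *The subgroup counts fail to match the ITT total.* SAP 3.4.4 limits the subgroup analysis to observed data without imputation, so its counts can fall short of ITT anyway. The adding-up complaint applies to the baseline table in 3.3.4, measured against the number with an HbA1c value.
- *The BMI groups are unworkable.* Followed by an explicit ≥30, the middle group is readily read as stopping below 30. Overlap needs the inclusive reading and categorising after rounding, and it touches about 2 participants.
- *The hs-CRP cut is wrong and empties the upper group.* The SAP uses mg/dL in both places, and nothing in the documents says mg/L was meant. Under the assumed distributions the upper group is usually small rather than empty. A small subgroup is not in itself an error.

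**Conclusion.** The HbA1c gap is a definite error of wording, shown by the text alone and not corrected elsewhere in either document. Its size rests on two assumptions: a normal distribution in the range above, and the reporting precision. It is about 15 to 30 of 300 participants if HbA1c is reported to one decimal, and about 7 to 15 if to two. The effect is confined to the HbA1c subgroup analysis and the HbA1c rows of the baseline table. The BMI wording is a minor tidy-up. The hs-CRP cut is a query about the unit and nothing more. The primary and secondary tests are untouched, so severity is low.

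**What to change.** - **HbA1c (SAP 3.3.4 and 3.4.4):** use <5.7%, ≥5.7% to ≤6.4%, >6.4%. If values carry two decimals, consider 5.7% to <6.5% and ≥6.5% instead. That would match the ≥6.5% limit in the new-onset diabetes definition in SAP 3.5.2 and settle where 6.41 to 6.49 belong. State the reporting precision.
- **BMI (SAP 3.4.4):** use <25, 25 to <30 and ≥30 kg/m².
- **hs-CRP (SAP 3.3.4 and 3.4.4):** confirm the cut against the laboratory's reporting unit and state it in that unit.

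The cost is SAP wording, with matching lines in the programming specifications. It should be done before unblinding so that no boundary is settled with treatment known. No data collection or sample size changes.
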